ART	Antiretroviral Therapy
ASO	AIDS Service Organization
ATN	Adolescent Medicine Trials Network for HIV/AIDS Interventions
CASI	Computer Assisted Self Interview
CDC	Centers for Disease Control and Prevention
CFR	Code of Federal Regulations
CHTC	Couples HIV Testing and Counseling
CRF	Case Report Form
CTR	Counseling, Testing, Referral
DCF	Data Collection Form
DHHS	U.S. Department of Health and Human Services
EC	Ethics Committee
GCP	Good Clinical Practices
HIPAA	Health Insurance Portability and Accountability Act
HIV	Human Immunodeficiency Virus
ICH	International Conference on Harmonization
IRB	Institutional Review Board
LGBTQ	Lesbian, Gay, Bisexual, Transgender, Queer
MC	Management Core
MTS	Michigan Tailoring System, a platform for eHealth interventions
NICHD	National Institute of Child Health and Development
NIDA	National Institute on Drug Abuse
NIH	National Institutes of Health
OHRP	Office for Human Research Protections
PI	Principal Investigator
PrEP	Pre-Exposure Prophylaxis
QNS	Query and Notification System
RDC	Remote Data Capture
SRV	Subject Recruitment Venue
STI	Sexually Transmitted Infection
TC	Technology Core
YGBMSM	Young Gay, Bisexual, and other Men who have Sex with Men
YMSM	Young Men who have Sex with Men

STUDY ABSTRACT

DESIGN:	
This project seeks to develop and pilot test a developmentally-appropriate HIV prevention intervention that includes relationship skills for young gay, bisexual and other men who have sex with men (YGBMSM). This project involves three phases to develop and pilot test the intervention. Phase I collects brief quantitative survey data, in-depth qualitative and cognitive interview data from YGBMSM, and feedback from a technical expert group (TEG) to develop and refine the intervention that comprises the We Prevent study. Phase II involves conducting a one-arm pilot of the intervention condition to further refine the intervention content with a sample of 24 YGBMSM (12 dyads). The final phase of We Prevent, Phase III, involves conducting a randomized controlled trial (RCT) comparing the relationship-focused intervention to a control condition, which is HIV Counseling, Testing, and Referrals (CTR) alone with a sample of 320 YGBMSM. This protocol is for Phase III of the proposed activities..

DURATION:	
Phase I is expected to take 7 months to complete. It includes data collection from two groups of participants: 1) 30 YGBMSM in in-depth interviews and 8 YGBMSM in cognitive interviews and 2) 7 Technical Experts, for a total sample of 45 research participants. Phase I is split into three tasks. For Task 1, 30 YGBMSM will be recruited through online banner advertisements and once consented and screened will complete a brief online survey which will take approximately 15-20 minutes to complete. Participants will then be invited to participate in an in-depth interview with a study staff member, which will take approximately 1-2 hours to complete. The data generated from Task 1 will be used to design the intervention manual. For Task 2, a technical expert group (TEG) of 7 individuals will be identified to participate in virtual meetings to review and provide feedback on the intervention content. For Task 3, an additional group of YGBMSM (n = 8), excluding those included in Task 1, will be recruited to complete cognitive interviews which will last approximately 1 hour to further refine the intervention. Phase II will consist of a one-arm pilot test of the intervention condition with 12 YGBMSM and their partners (total 24 participants). Each participant will complete baseline and 1-month follow-up surveys and all will get mailed STI testing kits at baseline. Phase III involves a two-arm prospective RCT in which 320 YGBMSM will complete surveys at Baseline, 3-month, 6-month, and 9-month follow-up. They will only be mailed STI kits at Baseline and 6-month follow-up. Participants randomized to the intervention arm will have the option to participate with their partner, though it is not required or necessary.

SAMPLE SIZE:	
Participants will be recruited online with potential representation from all 50 states. The sample size for Phase 1 is 45: this is comprised of 38 YGBMSM: 30 took part in in-depth interviews for

Task 1, and 8 took part in cognitive interviews for Task 3. For Task 2, 7 technical expert group members (TEG) were recruited to provide feedback on the intervention content. The sample size for Phase II is 24 participants (12 dyads), and the Phase III sample size is 320 participants.

POPULATION:

For phases I and II of the project, participants and their partners must be: (1) between the ages of 15 and 19 years (inclusive); (2) must meet the age of sexual consent in their states of residence (3) identify that they are in an emotional and/or sexual relationship with another male (assessed through multiple questions), (4) cisgender men (assigned male at birth and identifies as male) and transgender men (assigned female at birth and identifies as male or transgender man) who report intention to have sex with men; (5) report that they have engaged in any sex (oral, vaginal, anal) in their lifetime, (6) have access to personal device with internet access within their home, (7) self-report being HIV negative or unknown serostatus, and (8) speak or read English. A Technical Expert Group was formed in Phase I and consisted of members who engage with diverse communities of YGBMSM and have experience in the provision of HIV and LGBTQ clinical and social services. Phase III participants must (1) be between the ages of 15 and 24 years (inclusive); (2) meet the age of sexual consent in their states of residence (3) identify that they are in an emotional and/or sexual relationship with another male (assessed through multiple questions), (4) be a cisgender man (assigned male at birth and identifies as male) or transgender men (assigned female at birth and identifies as male or transgender man) who report intention to have sex with men; (5) report that they have engaged in any sex (oral, vaginal, anal) in their lifetime, (6) have access to a personal device with internet access within their home, (7) self-report being HIV negative or unknown serostatus, and (8) speak or read English.

Recruitment:

For all phases, we aim to recruit at least 50% racial and ethnic minority participants in all phases. In Phase III, we will stratify by race and ethnicity.

DATA COLLECTION:

For all study phases, YGBMSM will be recruited via online banner advertisements on social media (Instagram, Facebook, Snapchat) and will be connected to a screener survey via Alchemer. When a participant screens eligible in Phase II, they will provide their and their partners' contact information. After email and phone validation, they will be able to register for an account with the and will be enrolled in the study. Study staff will then send them each a link to complete the baseline survey. Once both partners have completed the baseline survey, the couple will schedule a relationship skills session that will be conducted via Zoom video-chat software. Zoom is a HIPAA-secure video-conferencing program. Once they have completed the relationship skills session, they will be mailed at-home HIV test kits and scheduled

for their CHTC session. Surveys will be completed at Baseline and 1-month follow-up. At-home STI testing kits will be offered at Baseline. Qualitative data will be audio-recorded, with participant consent, to allow for verbatim transcription of the interview and checked for accuracy and completion. A select number of participants (n=6) will be asked to complete an exit interview with study staff via Zoom. When a participant screens eligible for Phase III, they will be directed to a SMART registration page where they will complete the Baseline survey and be randomized. Those in the control condition will participate alone in a CTR session; those in the intervention arm will have the option to participate alone or with their partner in CTR + Relationship Skills and/or CHTC + Relationship Skills session(s). The HIV testing session will be conducted via Zoom, and the participant will complete follow-up surveys (3, 6, and 9 months) via Alchemer.

OBJECTIVES:

- 1) To develop and refine a developmentally appropriate relationship skills session as an additional session to the current CHTC and CTR interventions for 15-24-year-old YGBMSM.*
- 2) To conduct a randomized controlled trial (RCT) comparing the efficacy of the adapted intervention for YGBMSM versus a control condition, which is CTR alone.*

1.0 INTRODUCTION

1.1 Background

Young (15-24 years old) gay, bisexual and other men who have sex with men (YMSM) continue to be the group most heavily impacted by HIV in the US, despite stable or declining rates of infection among other groups.^{1,2} More than four decades into the epidemic, HIV prevention and research efforts in the US have continued to target MSM as individuals, largely focusing on messages that encourage the uptake of prevention efforts (traditionally condoms, and more recently PrEP) and reducing sexual risk. Recently, there has been growing interest in structural interventions to reduce HIV risk, tackling social, economic and cultural factors that place MSM in contexts of risk.³ However, despite socio-ecological theory postulating the importance of individual, dyadic and social influences on HIV risk, there has been a dearth of intervention efforts focused at the dyadic level. Substantial evidence indicates that one- to two-thirds of MSM acquire HIV from their main partners, and that the proportion of new infections attributable to main partners is higher (84%) among YMSM.^{4,5} Male couples' increase in HIV risk is attributed to a combination of a lack of knowledge of both partners' HIV status before engaging in condomless anal sex (CAS), higher number of anal sex acts between main partners, and more frequent receptive roles during anal sex acts.⁶⁻¹¹ CAS within relationships often occurs concurrently to CAS outside of the relationship, often as part of a mutual sexual agreement, potentially increasing the couples' risk for HIV and other sexually transmitted infections (STIs).^{7,8,12,13}

Although a number of evidence-based biomedical HIV preventive strategies exist for YMSM, uptake of these strategies within relationships remains low. Studies with HIV-negative male couples have found strong evidence that partnered men test less frequently for HIV and other STIs,¹⁴⁻¹⁶ and are less likely to adopt biomedical prevention strategies^{15, 28} and that their use is contingent upon their perception of risk.¹⁵ There has also been low awareness and uptake of PrEP which may be reflective of limited dissemination efforts of biomedical prevention strategies for young male couples,¹⁷ compounded with low perception of their HIV risk,¹⁸ and the uncertainty of how using a strategy may affect their relationship.¹⁹ Furthermore, many YMSM report increased fatigue with safer sex messages and practices but express a need for services that address health more generally,^{20,21} including relationship education services.²² Integrating relationship skills with HIV prevention is an important and necessary means to curb HIV incidence amongst those at highest risk for infection.

1.2 Rationale

To date, there are few scalable dyadic HIV prevention interventions exist for YMSM in relationships.^{3,23} Couples HIV Testing and Counseling (CHTC) has been shown to be as acceptable as individual HIV testing.²⁴ Despite widespread acceptability and utility,²⁵ there has been limited dissemination and scaling up of couples-based HIV prevention interventions for YMSM, including CHTC. Qualitative evidence suggests that YMSM have CAS with serious partners to express trust and intimacy, and they stop using condoms without initiating pre-exposure prophylaxis (PrEP) because they perceive that they are in a monogamous relationship.^{26,27} Young male couples also report infrequent HIV testing, even when CAS has occurred with outside partners.^{14,15} Because most existing prevention strategies focus in large part on reducing CAS with casual partners,²⁸ many YMSM do not have the skills to navigate the complexities of HIV prevention in romantic relationships, such as timing of HIV testing, condom use, and use of biomedical prevention strategies. Thus, incorporating relationship skills into existing the CHTC intervention delivered via video-counseling has the potential to empower YMSM with the skills necessary to communicate and protect themselves from HIV in their current and future relationships.

1.2.1 Telemedicine may provide an opportunity to address barriers to HIV testing for partnered YMSM.

YMSM often rely on online technologies to build their social and sexual networks, receive social support, and obtain relevant health information. In general, Internet use among young adults aged 15-29 is nearly universal, at 99% in 2016.^{29,30} Thus, telemedicine offers the opportunity to disseminate HIV prevention strategies to YMSM who might otherwise not have this opportunity. Telemedicine aims to circumvent traditional impediments to healthcare access. Over the past decade, telemedicine formats have been adapted for use in MSM populations where stigma and a lack of LGBT-friendly healthcare providers contribute to reduced access to care.³¹ Online interventions are seen as convenient for youth users and allow for home-based access to health messaging, thereby reducing fears of embarrassment or ‘outing’ by connecting with local resources.^{32,33,34}

1.2.2 Theoretical framework for We Prevent: Dyadic Intervention

We-Prevent draws on the Relationship-Orientation Information-Motivation-Behavioral Skills (RELO-IMB) model,³⁵ premised on the IMB model³⁶ and developed for YMSM communities.³⁷ The RELO-IMB model entails “Information” by addressing YMSM-specific knowledge (e.g., risk within

dyads and with outside partners), “Motivation” by addressing attitudes and peers norms about prevention in relationships, and “Behavioral Skills” by addressing risk reduction skills relevant to YMSM and their partners (e.g., discussion about safer sex, HIV testing, and negotiating safety in one’s sexual agreement). This study uses the RELO-IMB model, but with variations on specific measures in an effort to harmonize our metrics with other ATN studies. We Prevent includes two sessions: session one, a motivational interviewing guided session which provides a facilitated discussion between two YMSM in which they explore and understand their own HIV risk and learn behavioral skills to improve communication, and session two, a CHTC session between two YMSM which facilitates the development of a prevention plan that meets the goals of both partners. We hypothesize that YMSM and their partners who engage in We Prevent will demonstrate greater information about different prevention options (e.g., knowledge of PrEP and the importance of STI and repeat HIV testing). Furthermore, YMSM who engage in We Prevent will demonstrate greater communication skills to use in their relationship, which will provide them with greater self-efficacy for developing a HIV prevention plan with their partner. The use of motivational interviewing techniques will allow couples to realize areas where they are doing well in their communication and HIV prevention plan while highlighting areas for improvement. These skills will facilitate engaging in CHTC in the second session in which the two partners test together and develop a prevention plan. Thus, We Prevent will increase the uptake of HIV prevention strategies by exploring YMSM’s desires, goals and behaviors within their relationship and teaching YMSM models of communication and problem-solving strategies to help them enact effective communication towards HIV prevention planning and uptake. YMSM exposed to the intervention will learn about HIV prevention options (Information), HIV prevention and risk within relationships (Information and Motivation), and will practice communication and negotiation techniques towards the discussion of sex, sexual risk and HIV prevention and planning (Behavior).

2.0 STUDY OBJECTIVES

The overall objective of our program of research is to develop and test We Prevent (ATN Protocol #157), as part of the U19HD089881-02S2 UNC/Emory Center for Innovative Technology (iTech) across the prevention and care continuum project. Phase I and Phase II have already been approved by the UNC IRB and the objective of this proposal is to obtain approval for Phase III, which is the two-armed randomized control trial. For this application, we are requesting approval for Phase III procedures and materials only. The procedures and materials for Phase III rely on the findings from Phase II.

3.0 STUDY DESIGN

This four-year study consists of three phases to develop and test the “We Prevent” intervention for YMSM and their partners. Phase II and III protocols and procedures are premised on the formative data collected in Phase I; and Phase III has been further informed by the data collected in Phase II.

3.1 Study Population

For Phase I and II of this project, we recruited a diverse sample of 15-19-year-olds. For Phase III of the project, we will recruit a diverse sample of 15-24 year-olds. Age of recruitment will vary state-by-state due to variations in state sexual consent laws. Therefore, in some states we will

not be able to recruit participants who are as young as 15, and this state-by-state logic will be built into the screener.. We will exclude those who report a recent (6 month) history of intimate partner violence, using methods specifically designed for use with male couples. To ensure representation of racial/ethnic minorities, we have a target of 50% in all phases of the study be racial/ethnic minority participants. If enrollment of racial/ethnic participants drops below 50%, we will explore additional recruitment strategies.

Eligibility for both the participant and their partner will include the following: (1) between the ages of 15 and 24 years; (2) participants must meet the age of sexual consent in their states of residence; (3) identify that they are in an emotional and/or sexual relationship with another male (assessed through multiple questions, both at the individual and dyadic level), () born male or female and currently identify as male or transgender man, with an intention to have sex with men (5) report that they have engaged in any sex (oral, anal, vaginal) in their lifetime, (6) have access to personal device with internet access within their home, (7) self-report being HIV negative or unknown serostatus, and (8) speak and read English.

4.0 ELIGIBILITY AND SCREENING

4.1.a Inclusion Criteria for Phase I and II

*Below inclusion criteria must be satisfied by both participants within a dyad (i.e., both partners report that they are in an emotional and/or sexual relationship with each other).

- *Ages 15 to 19 years (inclusive) at time of screening*
- *Current US resident*
- *Sufficient age for sexual consent in the current state of residence*
- *Self-identify that they are in an emotional and/or sexual relationship with another male*
- *Cisgender men (assigned male at birth and identifies as male) and transgender men (assigned female at birth and identifies as male or transgender man) who report intention to have sex with men*
- *Self-reports that they engaged in some form of sex (oral, vaginal, anal) in their lifetime*
- *Has access to computer/personal device/smart phone with internet access*
- *Self-report being HIV negative or unknown serostatus*

- *Speak and read English*

4.2 Exclusion Criteria for Phase I and II

*Below exclusion criteria applies to both participants within a dyad

- *Younger than age for consent without parental permission in the current state of residence*
- *Assigned female sex at birth and currently identifies as something other than male or transgender male*
- *Assigned male sex at birth but identifies as gender other than male or transgender male*
- *Aged 14 years or younger or 20 or older at the time of screening*
- *HIV-positive*
- *Not currently in an emotional and/or sexual relationship with another male*
- *Does not speak or read English*
- *Reports intimate partner violence in the past 6 months*

4.3 Inclusion Criteria for Phase I, Task 2 (Technical Expert Group)

- *The individual has published in a peer-reviewed journal in the following domains in the past 4 years: HIV interventions for YMSM, online HIV interventions for YMSM, or dyadic HIV interventions.*
- *A list of potential participants will be identified through a review of the recent (4 year) literature.*

4.4 Inclusion Criteria for Phase III

*Below inclusion criteria must be satisfied by individual participants (or both participants within a dyad if they choose to participate as a couple, only in the intervention arm)

- *Ages 15 to 24 years (inclusive)*
- *Current US resident*
- *Sufficient age for sexual consent in the current state of residence (both at the individual and dyadic level)*
- *Self-identify that they are in an emotional and/or sexual relationship with another male*
- *Cisgender men (assigned male at birth and identifies as male) and transgender men (assigned female at birth and identifies as male or transgender man) who report intention to have sex with men*
- *Self-reports that they engaged in some form of sex (oral, vaginal, anal) in their lifetime*
- *Has access to computer/personal device/smart phone with internet access*
- *Self-report being HIV negative or unknown serostatus*
- *Speak and read English*

4.5 Exclusion Criteria for Phase III

*Below exclusion criteria applies to both participants within a dyad

- *Younger than age for consent without parental permission in the current state of residence*

- *Assigned female sex at birth and currently identifies as something other than male or transgender male*
- *Assigned male sex at birth but identifies as gender other than male or transgender male*
- *Aged 14 years or younger or 25 or older at the time of screening*
- *HIV-positive*
- *Not currently in an emotional and/or sexual relationship with another male*
- *Does not speak or read English*
- *Reports intimate partner violence in the past 6 months*

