4.6 Recruitment

All recruitment will be completed online: this protocol does not involve SRV engagement in recruitment or intervention delivery. Participants will be recruited via online ads placed on key social media websites (e.g., Facebook, Instagram, Snapchat, Grindr, etc.). The online ads will show visual representations of young male couples, in a range of race/ethnicities and will be titled: “*We Prevent.*” People who click on the advertisement will be taken to the Survey Gizmo screener webpage that provides basic information on the study: this will be referred to throughout the protocol as the ‘landing page’. On the landing page will be basic information on the study processes and a “do you consent to be screened?” question; if participants click “yes” they will be screened for eligibility.. All recruitment will be tracked in the screener with the question “How were you directed to the study website?”

This study will also use Cameo as part of its online recruitment strategy. Cameo is a website that allows users to pay celebrities to create short 20-second videos and deliver a particular message of the user’s choice. Once the video is created and paid for, Cameo delivers the video file to the user. Study staff will upload the video to the social media sites already being used for recruitment. The script will only contain information about the study: “Hi, this is (insert celebrity name) and I want to tell you about an HIV prevention study from the University of Michigan. This study is aimed at young gay and bisexual men who are in their first relationships. If you are eligible, you will take a few surveys and get mailed an at-home HIV testing kit. Click on the link to see if you’re eligible!”

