4.8 Screening and Registration

Participants will have completed the following process: clicking on a banner advertisement, learning about the study via the study landing page, consenting to be screened for eligibility, answering eligibility questions on a Alchemer survey, reading the informed consent/assent form and consenting/ assenting to participate. For participants in Phase III, after screening eligible, participants will be redirected to a SMART linked web page where they will enter their contact information, which will then be automatically populated into SMART and verified. Study staff members will verify eligibility for all participants who screen eligible and provide consent. Once their eligibility is confirmed, participants will be sent instructions to download the SMART study application and all follow-up activities will be conducted through SMART. If the participant is randomized into the intervention arm and chooses to participate with their partner, the invited partner will be emailed a link to the eligibility screener. If they screen eligible, study staff will schedule an informed consent phone call with the invited partner (described above in the informed consent section). Contact information for the invited partner will be requested in the brief baseline survey and will be stored in a password-protected file within Box or Microsoft OneDrive.

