5.5 Registration & Randomization (Phase III RCT)

In Phase III, after completing the baseline survey participants will be randomized via DFexplore in a 1:1 ratio into the intervention or control condition. In order for interventions to be evaluated as potential “best evidence”-based interventions through CDC’s Prevention Synthesis Research activity, data must be available for at least a single follow-up time point for at least 70% of participants. We will use best practices to retain participants (e.g., comprehensive locator information that includes participants' cell phone number, and e-mail), while being sensitive to undue disclosure of YMSM participating in the study. Depending on the participants' preferences provided upon registration, contacts will be made initially with the preferred mode of re-contact (for example, by SMS text message); if still unresponsive, other available modes (e.g., phone call) will be used. The study will use a HIPAA-compliant web-based platform entitled Study Management and Retention Toolkit (SMART), which is a SaaS (Software as a Service) based mobile application aiding studies with various aspects of participant recruitment, study implementation, and retention. SMART is a licensed service of the Center for AIDS Research (CFAR) at Emory University, Prevention Science Core. We will follow YMSM for 9 months and have contact with them every three months. The small time frames between assessments helps us to respond quickly to retention concerns. Incentives for completing the baseline and follow-up surveys will be \$40 per individual, per assessment. If a participant completes all three follow-up surveys, they will receive an additional \$40.

For both conditions, participants will be taken to an online calendar asking them to schedule their first session. The calendar will be populated by study staff per their availability and will reflect local time zones. The page will explain the session format, will provide detailed instructions on using the Zoom video-chat software, and will contain a list of instructions for participating in the sessions (e.g., audio and visual privacy, etc.). For both conditions, the

sessions will be about 45 minutes... Each session will be delivered via Zoom, the HIPAA-compliant video-chat software that can be used on a PC, tablet or smartphone.

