9.2 Compensation

Phase I participants will receive \$40 for completing the brief online survey and in-depth qualitative interview. Participants who complete the brief online survey and the cognitive interviews will also receive \$40. Phase II participants will receive \$40 for completing the baseline, \$50 for the follow-up assessment, and \$20 if they are selected to participate in an exit interview. Phase III participants will receive \$40 for each survey they complete, including the Baseline and all Follow-up surveys (3, 6, and 9 months). If a participant completes all three follow up surveys, they will receive an additional \$40. Invited partners will receive \$20 for completion of the brief survey. Participants that are selected to complete an exit interview will receive \$50. This is the standard compensation used by [name] in his ongoing YMSM studies.

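### Phase III has no stated rule or pre-randomisation check for two partners who both enrol as index participants, so a couple could be split across arms

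*Protocol*

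**What the plan says.** Being in a relationship with another male is a Phase III entry criterion (Protocol 4.4), but the unit that enters is the individual: "Below inclusion criteria must be satisfied by individual participants (or both participants within a dyad if they choose to participate as a couple", and the couple option exists only in the intervention arm. Protocol 3.1 sets one list of criteria for both members of a couple ("Eligibility for both the participant and their partner will include the following"). The exclusion list in 4.5 is headed "Below exclusion criteria applies to both participants within a dyad". Its eight items cover age (two items), sex and gender (two items), HIV status, relationship status, language and recent partner violence. None concerns a partner's enrolment.

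Recruitment is open and self-referred: "Participants will be recruited via online ads placed on key social media websites" (4.6). After the baseline survey, "participants will be randomized via DFexplore in a 1:1 ratio into the intervention or control condition" (5.5).

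For an intervention participant who chooses to involve his partner, "the invited partner will be emailed a link to the eligibility screener" (4.8). That partner completes a brief survey, is consented by phone and is kept outside SMART, the system that holds index participants (5.1). Protocol 5.1 also says that controls take part without a partner.

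The powered outcome is a 9-item scale of HIV-related dyadic communication (6.1).

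**The concern.** A trial that recruits people because they are in couples, and then randomises them singly, needs a position on two people from one couple. Without one, a man in the control arm may have a partner who is being taught communication skills in the intervention arm. The control's answers on a scale about communication with that partner could then move too, and the difference between arms would shrink. The same applies to someone who attended a couple session as an invited partner and later enrols as an index participant: if allocated to control, he has already received the intervention session.

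The documents make co-enrolment plausible, though not known. "The online ads will show visual representations of young male couples" (4.6), so one advertisement can appeal to both partners, and both face the same criteria. An index participant is paid 40 dollars for each of four surveys, and 9.2 adds: "If a participant completes all three follow up surveys, they will receive an additional" 40 dollars. That makes 4 × 40 + 40 = 200 dollars, against 20 for an invited partner.

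A second matter is that two people describing the same relationship give correlated answers, and the analysis text does not mention couples.

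**Working it through.** **Places where a safeguard could sit**

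- Protocol 4.4 and 4.5: no criterion on a partner who is enrolled, or on previous participation as an invited partner.
- Protocol 4.8: staff verify eligibility, but no comparison with other participants or their partners is described. Partner contact details are taken only through the invited partner's brief survey, so after randomisation and only in the intervention arm. They are kept in a separate file.
- Protocol 5.1: invited partners are not in SMART, so index participants and invited partners are on two lists. No step compares them.
- Protocol 8.2: a couple ID is listed for records. No use at screening, randomisation or analysis is stated.
- Protocol 11.2 and SAP: generalised estimating equations are described for repeated scores and 3-monthly counts. The couple is not named as a cluster.
- Contrast: Protocol 3.2 does state that the Phase I Task 3 sample must be independent of Task 1. Phase III has no counterpart.

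**Inputs for the size**

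- From the documents: 320 participants, so 160 per arm at 1:1; significance level 0.017, taken as two-sided because sidedness is not stated. The documents give no effect size, SD or power, so 320 cannot be reproduced.
- Assumed: f, the share of index participants in co-enrolled couples, 2% to 20%; c, the share of the effect passed to the control partner, 0.5 to 1; 80% power before dilution; no loss to follow-up.

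**Share of couples split.** Two independent 1:1 allocations differ with probability 1/2, so a share f/2 of controls has a partner in the intervention arm. For f = 5%, 10% and 20% that is 2.5%, 5% and 10%. A former invited partner who enrols gives the same half: his index partner is already in the intervention arm, and he is allocated to control with probability 1/2.

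**Dilution.** Remaining effect = 1 − c × f/2.

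- Smallest: 1 − 0.5 × 0.02/2 = 0.995, a dilution of 0.5%.
- Largest: 1 − 1 × 0.20/2 = 0.90, a dilution of 10%.

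**Power.** The standardised difference detectable with 80% power is (z for alpha + z for 80%) × √(2/160), which is 0.313 at alpha 0.05 and 0.361 at alpha 0.017. Multiplying it by the remaining effect and recomputing power gives the table below. The total needed to restore 80% power is 320/(remaining effect)², rounded up.

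| f | c | Remaining effect | Power, alpha 0.05 | Power, alpha 0.017 | N to restore |
|---|---|---|---|---|---|
| 2% | 0.5 | 0.995 | 0.7961 | 0.7955 | 324 |
| 5% | 1 | 0.975 | 0.7798 | 0.7766 | 337 |
| 10% | 0.5 | 0.975 | 0.7798 | 0.7766 | 337 |
| 10% | 1 | 0.95 | 0.7585 | 0.7518 | 355 |
| 20% | 1 | 0.90 | 0.7128 | 0.6980 | 396 |

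The loss runs from 0.4 to 10.2 percentage points.

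**Independence.** A t-test that ignores couples was simulated with 320 participants, nominal 5%, an assumed within-couple correlation of 0.5 and 20,000 runs. With partners allocated individually, type I error was 5.2% at f = 10% and 5.2% at f = 20%. The simulation error is √(0.05 × 0.95/20,000), about 0.15 points, so neither is clearly different from 5%. If every such couple were split, the figures were 4.5% and 3.9%; if every couple shared an arm, 5.9% and 6.1%. Individual allocation mixes the two, and they roughly offset.

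**The case against.** The strongest reply is that silence in two lists is not proof that co-enrolment goes unchecked. The screener is not in the documents, Protocol 3.1 says that the relationship is assessed by several questions at individual and dyadic level, staff verify every eligible applicant, and a couple ID exists. This stands in part: one can say that no rule or check is stated, not that none exists in practice.

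Four stronger readings are tempting, and the documents do not support them.

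- A reader might infer that controls can be expected at their partner's intervention session. Protocol 5.1 says that controls take part alone, and 4.4 confines the couple option to the intervention arm. What remains is that no step is described that would detect a control who is invited as a partner.
- A reader might infer that the screener link sent to invited partners feeds them into the randomised trial. As described in 4.7, 4.8 and 5.1, it leads to a phone consent call and a limited, non-randomised role.
- A reader might infer that the effect shrinks by the full share of exposed controls. That holds only if the whole effect passes to the control partner. Partner participation is optional (5.4), so partial transfer is at least as plausible.
- A reader might infer that correlated partners invalidate the tests. The simulation shows a negligible average effect under individual allocation.

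The upper end of the range for f also has no support in the documents. Recruitment is online, with potential representation from all 50 states, and co-enrolment may be rare.

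**Conclusion.** The gap holds as a low-cost improvement. The plan as written lets partners enter as separate index participants, or an invited partner enter later, and states no means of preventing, detecting or analysing this. The consequence that matters is dilution of the effect on a dyadic outcome. It is conditional on both partners enrolling. Its size, about 0.5% to 10% with a power loss of 0.4 to 10.2 points from an assumed 80%, rests entirely on the assumed ranges for co-enrolment and transfer. At 10% co-enrolment and full transfer, power would be about 76% at alpha 0.05 and 75% at alpha 0.017. The one-half chance of a split assumes that the two allocations are independent; stratified or blocked allocation could shift it somewhat. Non-independence is a minor matter of analysis and does not threaten validity.

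**What to change.** 1. Add two lines to Protocol 4.5: *current partner is, or has been, a Phase III index participant* and *has taken part as an invited partner*.
2. Add a screener question on whether the partner has enrolled. Also collect a minimal partner identifier from every applicant before randomisation, seen by staff only. This is needed because matching an applicant's own phone and email cannot link two partners who each came through an advertisement, and a self-report question alone is weak when payment depends on the answer.
3. Match each applicant against the invited-partner file before randomisation, and match each invited partner's contact details against SMART before the couple session.
4. For couples discovered after randomisation, state in the SAP a sensitivity analysis that clusters by couple or drops the second-enrolled partner.

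The sample size stays at 320. The cost is a few applicants lost, one more item from all applicants (including future controls, with matching consent wording) and a short addition to the eligibility verification that staff already carry out.
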